4.3 Study Enrollment Procedures

Recruitment will occur by way of flyers placed in well-trafficked areas, information sheets provided to potential participants, and clinician referral at partner practices. Women who express interest will be contacted by a study staff member to arrange for a virtual meeting (by phone or video) to obtain consent and complete the baseline assessment, if eligible. Consented participants will then be randomized, by the lead project coordinator using a standard randomization process, in equal proportions to receive the intervention (MMORE) or treatment as usual condition. The lead project coordinator will meet virtually with participants to explain the study procedures and provide instructions to the digital support features (Intervention Only).

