Treatment Retention. Self-reported adherence to medication for opioid use disorder will be assessed by an adaptation of items from the well-established Adherence to Medication questionnaire originally developed for assessing adherence to antiviral medications among persons with HIV/AIDS. (i.e., when was the last time you skipped buprenorphine medication? [past 2 days, within the past 2 weeks, 2-4 weeks ago, 1-3 months ago, never skipped past 3 months]. Participants will also report how often they attended group/individual counseling in the past 3 months [every week, every other week, once a month, less than once a month].

Opioid abstinence. The reliability of self-report of substance use for pregnant and parenting women is especially complicated due to well-founded fears of child protective service involvement and potential loss of children. That said, when research studies are well-conducted and assurances for protection of participant privacy are clear and conveyed with messaging informed by community partners with lived experience, women do reliably self-report their use behaviors.

Opioid use will be assessed with relevant items from the Alcohol, Smoking and Substance Involvement Screening Test, aligned with relevant timeframes (baseline: past 6 months, post-intervention and 3 month postpartum: past 3 months). Opioid use disorder severity will be assessed with items corresponding to DSM-V diagnostic criteria.

Secondary End Points:

Other substance use:

Self-reported frequency and quantity of opioid and other substance use (including alcohol, marijuana, and tobacco) will be assessed with the Alcohol, Smoking and Substance Involvement Screening Test, aligned with relevant timeframes (baseline: past 6 months, post-intervention, 3 month postpartum: since last survey).

Mental Health:

Depression will be assessed using the Edinburgh Prenatal and Postnatal Depression Scales, both of which have been used extensively with the target population.

Anxiety will be assessed with the Generalized Anxiety Disorder Scale (GAD-7)², a psychometrically sound instrument routinely used in general health care settings.

Stress will be assessed with the Perceived Stress Scale,³ a psychometrically sound instrument that has been used in other studies of contemplative interventions with pregnant women⁴⁻⁷.

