9.2 Sample Size and Randomization

Sample Size.

Aim 1: For the longitudinal models of binary outcomes (abstinence, retention), assuming a within-person correlation of 0.5, there will be 80% power to detect difference between arms in the proportion retained at the 3 timepoints if the average percentage retained in the TAU arm is 60%, and the average percentage retained in the MMORE arm is 79.2%. Similar power is obtained if the TAU arm has a retention percentage of 70% while the MMORE arm has a percentage of 87% across the three timepoints. In terms of comparing abstinence longitudinally, there will be 80% power to detect a difference between arms in the percentage abstinent at the 3 timepoints if the average percentage abstinent in the TAU arm is 80% while in the MMORE arm is 94%. Power for the comparison of number of weeks abstinent during the 8-week intervention period will be 80% (at the two-sided 0.05 significance level) for differences between arms that are 0.52 times a standard deviation or more. Analyses testing for differences between arms in changes between baseline and 8-weeks, will have 80% power to detect differences that are 0.40, 0.52, and 0.61 times a standard deviation, assuming within-person correlations of 0.7, 0.5, and 0.3, respectively. We will aim to recruit 150 participants to allow for attrition (20%).

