9.6 Data Analyses

Aim 1

Primary analysis: The difference between treatment arms with respect to likelihood of opioid abstinence and remaining in treatment will be evaluated by logistic generalized estimating equations (GEE). Since these binary outcomes will be evaluated at the 8-week as well as the 3-month postpartum time points, these GEE models will account for the non-independence of repeated measurements within individual. An indicator of treatment arm, time point, as well as an interaction between treatment and time point will be included as predictors in the model along with baseline covariates. Significant differences between the arms will be tested via contrasts involving the treatment*time point interaction term that compare the outcomes at each time point.

The impact of *MMORE* on treatment retention (number of weeks retained) will be evaluated via two-sample t-test if the distribution appears symmetric, but a non-parametric Wilcoxon rank sum test will be used otherwise.

Aim 2

Primary analysis: Analyses of mechanisms of effect of *MMORE* will be performed via parallel process growth models fit via structural equation models, and mediated effects between treatment assignment and outcome will be examined for the following mediator-outcome pairs: craving-abstinence, mindfulness-craving, mindfulness-treatment retention, depression-treatment retention, anxiety-treatment retention, stress-treatment retention, and mindfulness-pain. Since each mediator and outcome variable will be collected at multiple time points, latent intercept and slope effects can be estimated (as in latent growth curves). The parallel process growth models then examine mediation of the effect of an individual-level variable (treatment assignment) on the latent slope of the outcome variable by the latent slope of the mediator variable. For each mediator-outcome pair, a parallel process growth curve model will be fit including both the direct effect of treatment assignment to *MMORE* on the latent slope of the outcome, as well as the indirect effect of *MMORE* on slope of the outcome through the slope of the mediator. Estimates of path coefficients for each individual path as well as of the indirect effect along with a 95% bootstrap confidence interval will be obtained.

To examine these associations we will implement a newly developed modeling strategy called dynamic structural equation models (DSEM). DSEM like non-dynamic SEM are a modeling

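### Number of weeks retained is compared without baseline adjustment, although baseline items likely to predict it are already collected; the gain from using them depends on a correlation the plan does not give

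*Combined protocol and SAP*

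**What the plan says.** Treatment retention is one of two primary outcomes (sections 1.1 and 9.5.1). Section 6.2 builds it from weeks with buprenorphine or methadone in the urine screen and weeks of required counselling attended, counted through the prenatal period to 3 months postpartum. Section 9.6 (Aim 1) says that the count of retained weeks "will be evaluated via two-sample t-test if the distribution appears symmetric, but a non-parametric Wilcoxon rank sum test will be used otherwise". No covariate is mentioned.

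The binary versions of retention and abstinence are analysed by logistic GEE. There the plan states that an "interaction between treatment and time point will be included as predictors in the model along with baseline covariates". The covariates are not listed.

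For weeks abstinent, section 9.2 gives a power statement: "Power for the comparison of number of weeks abstinent during the 8-week intervention period will be 80" per cent, at a two-sided 0.05 level, "for differences between arms that are 0.52 times a standard deviation or more". Section 9.6 names no test for that count.

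On baseline data, the schedule in section 6.1 marks both opioid abstinence and MOUD treatment retention at baseline. The self-report survey in section 6.2 asks when medication was last skipped (five answer categories). On counselling: "Participants will also report how often they attended group/individual counseling in the past 3 months" (four categories). It also covers opioid use by ASSIST items, with a six-month look-back at baseline.

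**The concern.** Women who enter with recent skipped doses, irregular counselling or recent opioid use are likely to accrue fewer weeks of retention than women who enter stable. An unadjusted comparison leaves that predictable variation in the error term. It also makes no allowance for a chance imbalance in entry adherence between arms of about 60, and the permuted blocks in sections 6.2.2 and 9.2 are not described as stratified on any such factor.

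A smaller, related matter is that the choice between t-test and Wilcoxon rests on whether the distribution appears symmetric. That is a judgement made on outcome data with no stated criterion, and the two tests address different quantities.

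What is at stake is precision on a primary outcome in a trial of modest size, and a clear rule for how that outcome is tested.

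**Working it through.** **Inputs**
- Recruitment and attrition (section 9.2): "We will aim to recruit 150 participants to allow for attrition (20" per cent). So 150 × 0.80 = 120 analysed.
- Allocation (section 4.3): women are randomised "in equal proportions to receive the intervention (MMORE) or treatment as usual condition". So 60 per arm.
- Two-sided alpha 0.05, and 0.52 SD for weeks abstinent (section 9.2).
- Baseline-outcome correlation r for the weeks counts: not given. Section 9.2 uses 0.3, 0.5 and 0.7 for baseline-to-8-week change analyses and 0.5 for the binary models. I borrow 0.3 to 0.7 as an assumption and add 0.2, because the available predictors of weeks retained are proxies.

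**Step 1: reproduce the plan's figure**

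Noncentrality for a two-sample t-test = d × √(n/2) = 0.52 × √30 = 2.848, on 118 degrees of freedom. Power = 80.6% (81.3% by the normal approximation). The smallest difference detectable with 80% power, by the normal approximation, is (1.960 + 0.842) × √(2/60) = 0.51 SD. The plan's 80% at 0.52 SD is therefore what an unadjusted comparison with 60 per arm gives.

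**Step 2: add a baseline covariate**

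In a linear model, a covariate with correlation r to the outcome (the multiple correlation if several items enter) cuts residual variance by the factor 1 − r². The standardised difference becomes 0.52/√(1 − r²), here tested on 117 degrees of freedom with one covariate.

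| r | 1 − r² | 0.52/√(1 − r²) | Power | Gain (points, before rounding) |
|---|---|---|---|---|
| 0 (unadjusted) | 1.00 | 0.520 | 80.6% | – |
| 0.2 | 0.96 | 0.531 | 82.2% | 1.6 |
| 0.3 | 0.91 | 0.545 | 84.2% | 3.5 |
| 0.5 | 0.75 | 0.600 | 90.4% | 9.7 |
| 0.7 | 0.51 | 0.728 | 97.7% | 17.1 |

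In terms of detectable difference, r = 0.5 takes 0.52 SD to 0.52 × √0.75 = 0.45 SD, and r = 0.2 takes it only to 0.52 × √0.96 = 0.51 SD.

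**Step 3: what carries over to weeks retained**

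The table is built on the effect size for weeks abstinent over 8 weeks. Weeks retained is a different count over a longer window, and the documents give it no effect size, SD or correlation. The proportional variance reduction 1 − r² carries over; the power percentages are illustrative. The formula also treats the outcome as continuous and linear in the covariate, whereas weeks is a bounded count.

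**The case against.** The strongest reply is that an unadjusted t-test or Wilcoxon test is valid in a randomised trial. Chance imbalance does not bias it or inflate its type I error, and the plan's stated 80% for weeks abstinent is met without adjustment. That stands. The point is avoidable imprecision and an open choice of test, not an invalid analysis.

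A reader might infer that the plan throws away about 10 points of power. The documents do not support that as a fact. It needs r = 0.5, which is stated nowhere for the weeks counts, and it uses an effect size that belongs to weeks abstinent.

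A reader might also infer from the schedule that retention has a usable baseline value. Every woman must be receiving MOUD at entry (sections 4.1 and 5.3.2), so retention status is constant, and weeks accrued after entry have no baseline counterpart. What remains is coarse self-report set against a chart-and-urine outcome, and section 6.2 itself acknowledges that self-report of substance use is difficult in this population. The correlation may well be low.

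Pre-randomisation weeks from the chart might be a stronger predictor, but they are not shown to be free. The outcome as worded runs through the prenatal period and may already include those weeks. Adjusting for them would then put part of the outcome on both sides of the model. Section 6.2 also does not describe a separate extraction of that period.

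Finally, it is tempting to say that the GEE loses power by omitting baseline abstinence. The text does not say so. The GEE already includes baseline covariates and neither names nor excludes that one. If it is among them, nothing is lost.

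**Conclusion.** The point holds for number of weeks retained: the test is unadjusted and selected on the look of the data, while plausible predictors are collected at baseline. Adjustment would not bias the randomised comparison, and if the predictors prove weak almost nothing is lost.

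The size is a range, not a single figure. With 60 per arm and 0.52 SD, the illustrative gain is 1.6 points at r = 0.2, 3.5 at r = 0.3, 9.7 at r = 0.5 and 17.1 at r = 0.7. For weeks retained the low end may be nearer the truth. These values assume 20% attrition, a roughly linear relation and a correlation that the documents do not supply.

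There is also a gap in specification: weeks abstinent has a power statement in section 9.2 and no test in section 9.6. For the GEE, listing the covariates is a sensible clarification; no loss of power is shown there.

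**What to change.** In section 9.6, replace the t-test/Wilcoxon sentence with a prespecified regression of weeks retained on treatment, last skipped dose, counselling attendance and ASSIST opioid use, all from the baseline survey. Use ANCOVA with robust standard errors. If a rank ANCOVA is preferred for a skewed count, fix the rule for choosing it before outcome data are seen.

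Add the same form for weeks abstinent, with baseline opioid use as the covariate. State the window it covers, since section 9.2 powers the 8-week period while sections 6.2 and 9.5.1 count over longer periods.

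Use pre-randomisation chart weeks as a covariate only if the outcome window is first defined to start at randomisation and the extraction is planned.

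As a clarification, list the GEE's baseline covariates and name baseline opioid abstinence among them for the abstinence model.

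The cost is wording, one degree of freedom per item entered as an ordered score (out of 118), and a rule for missing baseline items. Randomisation follows completion of the baseline survey and section 9.3 analyses those who completed it, so the rule should mainly have to deal with single skipped items. The survey data are already planned for collection.

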1.0 STUDY OBJECTIVES

In this R33 phase of the project, we will conduct a randomized controlled trial to evaluate the efficacy and implementation of the *Mindful Moms* intervention with a sample of pregnant women with identified opioid use disorder receiving medication for opioid use disorder at partner maternity care practices. We will evaluate the impact of *Mindful Moms* as an adjunct to treatment as usual on retention in medication for opioid use disorder (MOUD) treatment, substance use, and relapse-related risks. This study has three Specific Aims:

Aim 1: Evaluate MMORE in a randomized controlled study with pregnant women as an adjunct to MOUD treatment as usual care for impact on treatment retention, opioid abstinence, and relapse risks.

Aim 2: Examine mechanisms of effect of MMORE on outcomes.

Aim 3: Evaluate barriers and facilitators to sustainable implementation of MMORE as an adjunct to MOUD for pregnant and parenting women.

1.1 Aim 1: Primary Objective.

To assess the efficacy of MMORE on maternal treatment and well-being outcomes.

Primary endpoints:

- 1) MOUD treatment retention
- 2) Opioid abstinence

Secondary endpoints:

- 1) Other illicit substance use
- 2) Psychological wellbeing (depression, anxiety, posttraumatic stress)
- 3) Mindfulness
- 4) Quality of life
- 5) Pain perception

1.2 Aim 2: Primary Objective.

To identify factors associated with change in endpoints to inform targets for intervention.

Primary endpoints:

- 1) MOUD treatment retention
- 2) Opioid abstinence

1.3 Aim 3: Primary Objective.

To identify barriers and facilitators to implementation of the intervention to guide development of strategies to overcome barriers in future work.

Primary endpoints: Endpoints for this non-powered exploratory aim are key implementation outcomes, including: 1) Intervention Acceptability, 2) Feasibility, 3) Fidelity, 4) Reach, and 5) potential for Sustainability within practice infrastructure.

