Aim 2: For examining mediation/mechanistic effects at the individual-level from longitudinal data via parallel process growth models (paths from treatment assignment to individual-level slope of mediator to individual-level slope of outcome), with 120 individuals, there will be 80% power to detect indirect effects comprised of a small-medium effects of the intervention arm on latent slope of mindfulness (defined as a correlation of 0.25 between variables or equivalently as explaining 6% of the variance in the latent mindfulness slope) and a medium effect of the slope of mindfulness on the slope of the outcome (defined as a correlation of 0.36 or equivalently as explaining 13% of the variance of the outcome). For examining mediation/mechanistic effects at the weekly level, power is less clear. Although DSEM combines aspects of more familiar modeling techniques, it is new and thus limited information is available on determining power for such models. In one set of simulation studies, good model performance was observed for several models differing in complexity for a sample size of 200 individuals with a number of observations per individual ranging from 20-200, and good model performance for all but the most complex models for smaller sample sizes. Thus, with data from 120 individuals contributing up to 8 observations each, we expect to have enough data to accomplish the aim of understanding the mechanisms underlying the intervention effects of MMORE. We will conduct weekly assessments to minimize participant burden. This strategy will still allow us adequate sampling frequency to track changes in outcome measures over the course of treatment. The power

calculations for the mechanistic effects were based on individual-level latent slope variable estimates and are thus not affected by a change to the number of indicator variables for the latent slope variables (reduced from 70 daily assessments to 8 weekly assessments). Power calculations for the dynamic SEM models are approximate and were not specifically based on having daily assessments per individual so will also not change.

Aim 3 is exploratory and not powered.

Treatment Assignment Procedures

Randomization will be conducted via permuted blocks. Once 8-10 participants have enrolled, an intervention will commence for that cohort. The randomization block size would be random, with blocks of size 4, 6, and 8. We plan ongoing recruitment and to start a new group approximately every 8 weeks.

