framework that allows for estimating simultaneous sets of equations involving latent and observed variables, thus allowing modeling of multi-level data, and modeling relationships at each level including mediation. Unlike non-dynamic SEM, however, DSEM have the capability to estimate time-series model(s) at the within-individual level, and also allow for a between-time level model (in addition to the between-individual level model) to incorporate time-varying effects observed in intensively collected data (i.e. creating a cross-classified model). Thus DSEM combine the advantages of time-series models, multi-level models, time-varying effect models, and other SEM, and importantly for the current application allows examination of relationships between multiple intensively collected variables (here affective state, mindfulness, stress, and craving) as well as moderation of these relationships by both individual-level (here treatment arm) and daily-level (session attendance, mindfulness) variables. The DSEM is specified by models at three levels. The three-level specification results from a decomposition of the observed variable(s) for a given individual at a given time (vector Y_{it}^*) into three latent, unobserved parts: an individual-specific contribution $Y_{2,i}$ a time-specific contribution $Y_{3,t}$ and a deviation for an individual, at a given time $Y_{1,it}$ ($Y_{it}^* = Y_{1,it} + Y_{2,i} + Y_{3,t}$). For example, for stress, observed weekly stress ($dStr_{it}^*$), becomes: $dStr_{it}^* = dStr_{it} + Str_i + Str_t$. These three latent components are then modeled simultaneously in a within-individual, between-individual, and between-time model. The time series describing the relationship between past and current observations in one or more intensively collected variables is modeled at the within-individual level (detailed below) The between-individual model examines influences on mean weekly stress (Str_i) and mean weekly craving as well as influences on individual-level random effects specified in the within-individual model (e.g. $\varphi_{SC,i}$: representing the relationship between weekly craving and weekly stress). The between-time model examines influences on the mean daily stress at a given time (Str_t) and on mean weekly craving at a given time (as well as influences on time-specific random effects specified at the within-individual model). For the current application, one within-individual model is a bivariate autoregressive (here specified with a lag of 1 but other lags will be explored) of weekly stress ($dStr_{it}$) and weekly craving (dCr_{it}).

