
$$\begin{aligned} dStr_{it} &= \varphi_{SS,i} dStr_{it-1} + \varphi_{SC,i} dCr_{it-1} + \zeta_{S,it} \\ dCr_{it} &= \varphi_{CC,i} dCr_{it-1} + \varphi_{CS,i} dStr_{it-1} + \zeta_{C,it} \end{aligned}$$

We will obtain an estimate of the relationship between the current value of dCr and lagged value(s) of dStr ($\varphi_{CS,i}$). Moderation of this relationship by immediate contextual variables (such as weekly mindfulness value, mindfulness session attendance (among those on MMORE arm)) can be examined by including an interaction between time-varying context variables and dCr in the dStr equation. Since the regression parameters estimated are considered random individual effects, associations with other individual-level variables (such as treatment arm assignment) can be modeled in the between-individual model. This will allow us to examine moderation of the weekly relationship between dStr and dCr by individual-level variables. Mediation of the effect of immediate contextual variables on mRB by mSR will be evaluated using a cross-lagged mediation model.

Aim 3 (Exploratory). Quantitative data will be descriptively summarized, and qualitative data coded for salient themes using standard deductive methods described earlier. Data summaries will be reviewed by the Steering Committee and consultants to inform strategies to support dissemination and sustainable implementation of MMORE in women's health care settings. Data will guide interpretation of participant outcomes.

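### Aim 2 never estimates the effect of MMORE on opioid abstinence through mindfulness, and the craving-to-abstinence path is left unadjusted for mindfulness

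*Combined protocol and SAP*

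**What the plan says.** Section 1.2 states the Aim 2 objective as "To identify factors associated with change in endpoints to inform targets for intervention" and lists two primary endpoints, MOUD treatment retention and opioid abstinence.

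Section 9.6 (Aim 2) lists seven pairs: "craving-abstinence, mindfulness-craving, mindfulness-treatment retention, depression-treatment retention, anxiety-treatment retention, stress-treatment retention, and mindfulness-pain". Mindfulness is the mediator for craving, retention and pain. Abstinence appears once, with craving as its mediator. For each pair, "a parallel process growth curve model will be fit including both the direct effect of treatment assignment", together with one indirect path through that pair's mediator. No second mediator or covariate is named. Path coefficients are to be reported, and the indirect effect gets a 95% bootstrap interval.

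Section 9.2 says that "with 120 individuals, there will be 80% power to detect indirect effects" made up of an arm-to-mindfulness-slope correlation of 0.25 and "a medium effect of the slope of mindfulness on the slope of the outcome", set at 0.36. The outcome is not named.

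The dynamic structural equation models in 9.6 cover weekly variables ("here affective state, mindfulness, stress, and craving"), and abstinence is not among them. In the stress-craving model mindfulness enters as a moderator: "Moderation of this relationship by immediate contextual variables (such as weekly mindfulness value". The section's one sentence on dynamic mediation reads "Mediation of the effect of immediate contextual variables on mRB by mSR will be evaluated using a cross-lagged mediation model". Neither mRB nor mSR is defined in the documents.

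**The concern.** Mindfulness is what the intervention trains and what the Aim 2 power statement is built on. It is tested as a mediator for one Aim 2 primary endpoint and not for the other, and no reason is given. The links from mindfulness to craving and from craving to abstinence are each fitted, but in separate models. Neither the chain nor any mindfulness-abstinence route outside craving is therefore estimated.

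A second consequence is conditional. By listing mindfulness-craving, the plan treats mindfulness as a cause of craving. If mindfulness also affects abstinence in other ways, it is a common cause of mediator and outcome in the craving-abstinence model. The background makes such routes plausible: section 2.2 says mindfulness programmes address other internal states that prompt use as well as craving, and section 2.1 links under-treated pain to relapse. Randomisation and the direct arm term do not remove this, because mindfulness also varies within arm.

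At stake is how far the trial can say which targets matter for abstinence. A craving coefficient that carries part of a mindfulness effect could make craving look a better target than it is.

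**Working it through.** **Inputs from the documents.** N = 120 (150 recruited less 20%), 1:1 allocation, arm-mindfulness correlation 0.25, mindfulness-outcome correlation 0.36. Two-sided 0.05 is stated for Aim 1 and assumed for Aim 2.

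**Assumed inputs.** Mindfulness-craving g = -0.36 (the plan's medium value, borrowed). Direct mindfulness-abstinence path d = 0.10 to 0.36. True craving effect on abstinence = 0. The arm moves craving only through mindfulness. Slopes are standardised, linear and treated as observed.

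**1. The plan's own power figure.** Fisher-z power for each link:
- arm to mindfulness: atanh(0.25) × √117 = 2.76; Φ(2.76 - 1.96) = 0.789
- mindfulness to outcome, given arm: atanh(0.36) × √116 = 4.06; Φ(4.06 - 1.96) = 0.982
- product: 0.789 × 0.982 = 0.775

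Simulation (2,000 trials) gives 79.6% by joint significance and 79.4% by percentile bootstrap. The stated 80% is reproduced.

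**2. Bias in the craving-abstinence coefficient when mindfulness is omitted.** With arm in the model:

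bias = d × g × (1 - 0.25²) / (1 - (0.25 × g)²) = d × (-0.36 × 0.9375) / (1 - 0.0081) = -0.340 × d

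With a standard error of about 1/√117 = 0.092, the chance that this path is falsely significant is Φ(z - 1.96) + Φ(-z - 1.96), where z = |bias|/0.092.

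| d | bias | z | falsely significant |
|---|---|---|---|
| 0 | 0 | 0 | 5% |
| 0.10 | -0.034 | 0.37 | 6-7% |
| 0.25 | -0.085 | 0.92 | 15% |
| 0.36 | -0.122 | 1.33 | 26% |

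Simulation agrees: about 6% at d = 0.10, 15% at 0.25 and 27% at 0.36. If craving truly acts at -0.36 and d = 0.36, the path is estimated at -0.48.

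**3. The whole indirect effect.** The joint test also needs the arm-to-craving link. Here that correlation is 0.25 × 0.36 = 0.09, detected in about 16% of trials. At d = 0.36 the false-positive rate is therefore about 0.16 × 0.27 = 4%, and simulation gives 4%. Across d = 0.10 to 0.36 it is about 1% to 5%. It rises only under stronger assumptions: 12% at g = -0.50, d = 0.36, and 20% at g = -0.50, d = 0.50.

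**4. After the change.** An added mindfulness-abstinence pair at 0.25 and 0.36 has the power in step 1, about 78% to 80%. A serial effect with a further assumed 0.36 link has about 76% by the same product. The chance of any false positive among independent, unadjusted tests goes from 1 - 0.95⁷ = 30% to 1 - 0.95⁸ = 34%.

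**The case against.** A short, prespecified pair list is a legitimate choice. The stated objective does not require mindfulness to be tested against every endpoint, and mindfulness is tested against retention, craving and pain. The generic outcome in section 9.2 fits those listed pairs. All of this stands: a reader might infer that 9.2 and 9.6 contradict each other, or that the 80% is wrong, and the documents support neither. What remains is an unexplained gap for one of two primary endpoints.

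The bias rests on an assumed path. The 0.36 in 9.2 is a whole mindfulness-to-outcome effect, so it is generous as a residual direct path, and at 0.10 the error rate is close to nominal. This also stands.

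A reader might take 27% as the error rate of the craving mediation test. It is not: it belongs to one coefficient, while the mediated effect is judged on the bootstrap interval for the indirect effect. The coefficient still matters, because individual paths are to be reported.

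Every listed pair is a one-mediator model, so stress, mood or pain could confound craving-abstinence too, and adding mindfulness is only a partial remedy. Slopes over the same weeks cannot establish that mindfulness changes before craving. Both points are fair and limit what the remedy can claim.

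The cross-lagged mediation sentence might be thought to cover the gap. With its outcome and mediator undefined, it cannot be read as a mindfulness-abstinence analysis.

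**Conclusion.** The omission holds on a plain reading of section 9.6: as written, no analysis estimates the effect of MMORE on abstinence through mindfulness. That does not depend on any assumption about bias.

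The confounding point holds only conditionally. It requires a mindfulness effect on abstinence outside craving, and with none the bias is zero. Under the assumptions listed, the craving-to-abstinence coefficient is shifted by about -0.03 to -0.12 and falsely significant in about 6% to 27% of trials. The full indirect effect stays at or below about 5%, provided the arm moves craving only through mindfulness. The stronger conclusion, that the planned craving mediation result is invalid, is not supported.

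This is a worthwhile, inexpensive improvement to a mechanistic aim. It does not affect the Aim 1 comparison or the sample size.

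**What to change.** In section 9.6, add mindfulness-abstinence to the pair list. Fit the craving-abstinence model with the mindfulness slope as a second mediator, so that mindfulness and craving are modelled jointly. Report each specific indirect effect with the 95% bootstrap interval already planned. A serial mindfulness-craving-abstinence effect may be reported as exploratory, with the caveat that the slopes cover the same weeks.

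The data are already to be collected: weekly mindfulness and craving items, and weekly urine screens from the clinical record. The cost is one more test, with no multiplicity rule stated for Aim 2 (30% to 34% as above), and a slightly larger model. Power for the added pair of about 78% to 80% treats slopes as observed; latent slopes or a binary abstinence outcome would lower it.
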